2.11.1.10. Quality of life, neurocognitive outcome and psychosocial functioning

QoL in craniopharyngioma patients can be affected by both the tumor itself and the treatment received. Reports assessing psychosocial and physical functioning show variable results, ranging from excellent in a majority of subjects to impaired function in almost half of the patients [24, 140, 214-217]. The most common areas of difficulty reported include social and emotional functioning, with patients rating their psychosocial status to be lower than their physical health [140]. Other reported challenges included somatic complaints such as reduced mobility, pain, and self-care [52, 140]. Behavioral questionnaires indicate a high rate of psychopathological symptoms, including depression, withdrawal, and anxiety. The most frequent problems in children's everyday functioning include difficulties in learning, inability to control emotions, unsatisfactory peer relationships, and concerns regarding physical appearance and body image [148, 218].

Reported factors associated with worsening quality of survival outcomes as well as neurocognitive and psychosocial functioning include younger age at diagnosis and preoperative functional impairment. Furthermore, tumor characteristics - including larger tumor volume, hypothalamic and 3rd ventricle involvement at presentation - are reported in the literature to complicate both pre- and post-surgical conditions and therefore survival and QoL outcomes in these patients [33, 40, 139, 219]. Treatment strategies have also been implicated with worse outcomes for surgery alone compared to limited surgery followed by irradiation and for multiple operations for tumor recurrence. Endocrine, neurological, and ophthalmological sequelae all adversely affect QoL outcome [24, 52, 136, 137, 140, 214, 215]. Hypothalamic dysfunction has been found to have the most important negative impact on social functioning, physical ability, and body image [140, 155, 215].

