The literature on neuropsychological conditions of craniopharyngioma patients appears to be controversial based on a small investigative collective and a variety of study methodologies [263]. Data on preoperative neuropsychological conditions are rare and studies on postoperative, neuropsychological outcomes are frequently extremely difficult to interpret in the absence of preoperative baseline investigations. Comparative evaluations of pre- and postoperative neuropsychological deficits are key to planning surgical strategies (gross total resection vs. partial resection plus immediate irradiation) with regard to long-term QoL effects.

The predominant indicator found in the literature is postoperative normal intelligence quotients (IQ) for adult craniopharyngioma patients [24, 264], yet only anecdotal reports have been published on diminished postoperative intelligence results [265, 266]. Honegger and colleagues prospectively studied a small collective (n=13) of adult craniopharyngioma patients following mostly transsphenoidal resections and found no impairments regarding their neuropsychological status [267]. However, several studies of children with craniopharyngioma yielded disturbances of memory, attention, impulse control, motivation and socialization [268-273]. The correlation between cognitive interferences and radical resection remains controversial [271, 274]. It is generally agreed that neuropsychological consequences following irradiation are dependent upon the child's age, irradiation volume, individual dosages, fractionated method and the total dosage, as well as illness-contingent and other therapy-associated variables. Neuropsychological deficits appear more serious in patients following relapses and/or relapse surgery [275]. As of yet there are no published prospective investigations regarding neuropsychological prognoses of children and adolescents with craniopharyngioma.

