4.2. Statistical endpoints and independent variables

The present protocol is a prospective, multicenter registry with the goal to observe and analyse multidisciplinary treatment approaches in childhood-onset craniopharyngioma. Therefore, several endpoints were chosen that reflect patients' survival and QoL. The association between these endpoints and a set of independent variables that represent diagnostic characteristics and treatment strategies will be analysed. On the basis of previous analyses (e.g., KRANIOPHARYNGEOM 2000 / KRANIOPHARYNGEOM 2007), the independent variables have been divided into two categories according to their expected influence on outcome and prognosis of childhood-onset craniopharyngioma.

Endpoints: - Overall survival (OS) defined as time from diagnosis to death

- Progression-free survival (PFS) defined as time from diagnosis to progression or death (whichever occurs first)
- Quality of life (PedQol, PedsQL, FMH)
- Degree of obesity (BMI SDS)

Factors of influence (mandatory):

- Tumor location (grade of hypothalamic involvement, grade 0-2)
- Neurosurgical treatment strategy (intended radical resection vs.
- incomplete resection + XRT)
- Realized degree of surgical resection (complete resection vs. incomplete resection)
- Postsurgical hypothalamic lesions (grade 0-2)
- Irradiation: modality (photon vs. proton beam therapy) and treatment (dose)

Factors of influence (potential):

- Clinical manifestations and symptoms in history
- Duration of history
- Histology (adamantinomatous vs. papillary type)
- Hydrocephalus at diagnosis
- Patient load of treating neurosurgical units (based on patient load during 10 yrs)
- Patient load of treating radiotherapy units (based on patient load dring 5 or 10 yrs)
- Tumor structure in imaging (tumor volume, cysts, calcifications)
- Endocrine deficiencies (number of deficient hypothalamic-pituitary axes)
- Growth hormone substitution (patient age at initiation, duration)
- Ophthalmological deficits (visual acuity, perimetric deficits)
- Neuropsychological findings, memory deficits, cognition (HIT-Basisdiagnostikum)

- Eating disorders (IEG)
- Experimental therapeutic approaches for obesity treatment (GLP-1R Agonists, Oxytocin)
- Other experimental therapeutic approaches, e.g. intracavitary therapy (intracystic IFN- α)

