4.3. Statistical analysis

The analysis of the data collected in this registry will be mainly descriptive. All inferential analyses will be regarded as exploratory (hypotheses generating) and will be interpreted accordingly. The aim of the analyses is to describe the frequency and modality of treatment approaches and to investigate their influence on survival and QoL. Since the planned study is a purely observational study, no randomized comparisons of treatment strategies are possible. Therefore, in addition to univariable analyses, multivariable analysis strategies are used to take account of different baseline risks due to different demographic or diagnostic characteristics. The model selection in the mutivariable analyses can be done by clinical considerations or by means of automated selection as likelihood-ratio based stepwise selection procedures.

Continuous variables (e.g., BMI SDS, QoL) will be summarised using the following descriptive statistics: n (non-missing sample size), number of missing values, mean, standard deviation, median, Q25%, Q75%, maximum and minimum. Histograms or boxplots will be used for graphical presentation of data. For the comparison of independent groups, statistical tests appropriate to the statistical distribution of the particular endpoint will be used (e.g., Student's t-test, Mann-Whintey U-test). To assess the difference of measurements between two different time points, statistical tests as Student's t-test for paired samples, Wilcoxon signed-rank test, or the sign-test will be applied. For comparison of more than two successive measurements, methods accounting for intra-individual correlation will be used (e.g., Linear Mixed Models), additionally adjusting for potential confounders.

Time-to-event endpoints as OS and PFS will be analysed descriptively using the Kaplan-Meier method. Groups will be compared using the log-rank test. Multivariable analyses will be performed using Cox proportional hazard regression analysis.

For categorical variables, the frequency and percentages (based on the non-missing sample size) of observed levels will be reported. Bar charts will be used for graphical presentation of data. The association of a categorical outcome and categorical independent variables will be analyszed using Fishr's exact test or the χ^2 test.

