6.1. Checklist: Preoperative diagnostics

Anthropometric data

- O weight
- O height
- O waist circumference
- O Tanner puberty stage (PH I-IV, B I-IV)

Ophthalmological staus

- **O** visual acuity
- O optic nerve and optic disc examination
- **O** visual field

Neuroradiological Imaging

- O MRI before and after contrast agent
- O CT limited scans of the sellar area without contrast agent

Laboratory testing

- O diabetes insipidus diagnostics (fluid intake / urine output, 1st morning urine osmolality
- O serum prolactin
- $\mathbf{O} \alpha_1$ -fetoprotein and β -hCG in serum
- O thyroid parameters (fT4, TSH)
- O serum/salivary cortisol profile or free cortisol in 24h urine collection

Documentation forms (see CRFs - Appendix section 16)

Functional capacity

O Fertigkeitenskala Münster-Heidelberg (FMH)

Neuropsychological assessment if feasible (basisdiagnostikum of HIT trials)

- O Bayley Scale of Infant and Toddler Development III (BSID III)
- O Coloured Progresses Matrices (CPM/SPM)
- O Kaufmann Assessment Battery for Children (K-ABC)
- O Hamburg-Wechsler Intelligence Test for Children IV; -Adults (HAWIK IV/HAWIWA/WIE)
- O Developmental Test of Visual-Motor Integration (VMI)
- O Continuous Performance Test (CPT)
- O Child Behavior Checklist (CBCL)
- O specific neuropsychological assessment (s. page 47)

Quality of life (if possible!)

- PedQol 8 18-yr or 4 7-yr (patient and parent version)
- PedsQL (patient and parent version)

Intraoperative asservation of CSF, cyst fluid, tissue for tumor bank

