6.3. Optional diagnostics at primary diagnosis

Optional procedures	Parameters
endocrine testing	preoperative endocrine deficits
neuropsychological diagnostics	preoperative baseline assessment
QoL (PedQol)	preoperative baseline assessment

Objectives of preoperative diagnostics

- Imaging confirmation of suspicious diagnoses as well as differential diagnosis with regard to other sellar/parasellar masses, as well as description of tumor dimensions and confirmation of cysts and/or calcifications for surgical planning
- Diagnosis of existing preoperative endocrine deficits needing immediate hormonal substitution treatment (DI, hypocortisolism)
- Ophthalmological assessment of vision acuity, field of vision and existence of papilledema
- Baseline assessment of preoperative conditions (anthropometry, neuropsychology and healthrelated QoL)

Anamnesis

Preoperative information on patient history as well as parental auxiological case histories should be compiled (see MARWIN forms).

Clinical findings / anthropometric data

a. Complete physical and neurological investigation

Assessment of pubertal stage (Tanner pubertal stage). Volume (ml) of both testicles using Prader orchiometer.

b. Anthropometric measurements

Height and weight:

• Patient's **height** should be measured in upright standing position using a stadiometer. Baby and infant length measurement (up to 2-yrs of age) is taken while baby/infant is in lying position. Height/length value is averaged based on three consecutive measurements.

• Waist circumference should be measured midway between the lowest rib and the top of the iliac crest at the end of gentle expiration. Circumferences were measured over the naked skin and noted to the nearest 0.1 cm. Infants were measured in the supine position.

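### Preoperative FMH, PedQol and PedsQL scores are in neither factor list of section 4.2, so non-randomised comparisons of these endpoints at follow-up may carry residual confounding by preoperative function

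*Protocol*

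**What the plan says.** Section 4.2 of the protocol names "Quality of life (PedQol, PedsQL, FMH") among the endpoints. It then gives two lists of independent variables, mandatory and potential, sorted by expected influence on outcome. Neither list contains the preoperative score of any of the three instruments, and nor do the matching lists in the Synopsis.

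The scores are requested before surgery:
- The checklist in 6.1 has "Fertigkeitenskala Münster-Heidelberg (FMH") under functional capacity, without qualification. It has PedQol and PedsQL under "Quality of life (if possible".
- PedQol appears again in 6.3, under the title "Optional diagnostics at primary diagnosis". The objectives given there include "Baseline assessment of preoperative conditions (anthropometry, neuropsychology and healthrelated QoL").
- After surgery, section 8.1 schedules QoL and FMH at three months and then yearly.

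Section 2.11.1.10 says that reported factors for worse quality of survival and psychosocial functioning "include younger age at diagnosis and preoperative functional impairment".

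On analysis, section 4.3 states: "For the comparison of independent groups, statistical tests appropriate to the statistical distribution of the particular endpoint will be used". The t-test and the Mann-Whitney test are its examples. It also plans paired tests for two time points, linear mixed models for more than two (adjusted for confounders it does not name), and multivariable models for demographic or diagnostic differences. Section 4.4 rules out imputation in the primary analyses and allows multiple imputation in sensitivity analyses.

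**The concern.** The registry wants to learn how treatment strategy influences QoL, and strategy is not randomised. The Introduction describes individual, risk-adapted treatment. If children treated by one strategy start with better function than those treated by another, part of that difference will still be present at follow-up and can be read as an effect of strategy.

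The preoperative score of the same instrument is the most direct adjuster, and the protocol asks for it as a baseline. In section 2.11.1.14 it says that postoperative neuropsychological studies are "frequently extremely difficult to interpret in the absence of preoperative baseline investigations". That remark concerns neuropsychology, but the same reasoning applies to QoL. Nothing in 4.2 or 4.3 says that the score will be used when strategies are compared. If stepwise selection is run on the listed factors, it cannot pick up a variable that is not listed.

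**Working it through.** The protocol gives no sample size, power, effect size, SD or correlation for a QoL comparison, so there is no figure to reproduce. The sizes below rest on assumptions.

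**Inputs from the protocol.** 30 craniopharyngioma patients per year (Synopsis). Longitudinal QoL in 41 of 70 patients in the predecessor study (2.11.1.16), used here only to illustrate possible baseline coverage: 41/70 = 0.586.

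**Assumptions.** Baseline-to-follow-up correlation ρ of 0.3 to 0.7; baseline imbalance δ of 0.2 to 0.5 SD; five years of accrual, 5 × 30 = 150 patients, in two equal groups of 75; two-sided 5% tests; equal SDs at both times.

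**1. Bias with no other adjustment.** Bias ≈ ρ × δ, in SD units.

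| ρ | δ = 0.2 | δ = 0.3 | δ = 0.5 |
|---|---|---|---|
| 0.3 | 0.06 | 0.09 | 0.15 |
| 0.5 | 0.10 | 0.15 | 0.25 |
| 0.7 | 0.14 | 0.21 | 0.35 |

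**2. Effect on a test when strategy has no effect.** The test statistic shifts by s = ρδ/√(2/75), with √(2/75) = 0.163. The rejection rate is 1 − Φ(1.96 − s) + Φ(−1.96 − s). At δ = 0.3, s is 0.55, 0.92 and 1.29 for ρ = 0.3, 0.5 and 0.7. The rejection rates are 8.5%, 15.1% and 25.1%, against a nominal 5%.

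**3. Precision with a complete baseline.** Residual variance is multiplied by 1 − ρ²: 0.91, 0.75 and 0.51. For a 0.5 SD difference at 80% power, patients per group fall from 63 to 58, 48 and 33.

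**4. Precision with an incomplete baseline and no imputation.** A covariate model then uses complete cases only. Its SE relative to the unadjusted SE is √((1 − ρ²)/0.586): 1.25, 1.13 and 0.93. Break-even is at ρ = √(1 − 41/70) = 0.64. Power for a 0.5 SD difference with 75 per group is:

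| ρ | Unadjusted | Baseline complete | Complete cases at 41/70 |
|---|---|---|---|
| 0.3 | 86.5% | 89.4% | 69.0% |
| 0.5 | 86.5% | 94.2% | 77.2% |
| 0.7 | 86.5% | 99.0% | 90.7% |

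**5. Two ways to use the baseline.** If the follow-up difference is effect + ρδ, the difference in change from baseline is effect + ρδ − δ, that is effect − (1 − ρ)δ. At δ = 0.3 this is off by −0.21, −0.15 and −0.09 SD. If instead the starting gap would have persisted unchanged without any effect of strategy, the change comparison is right and covariate adjustment is not. The two approaches differ whenever the groups start apart.

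**The case against.** Several points on the other side are sound.

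- A reader might infer that the preoperative value is used only in within-patient paired tests. Section 4.3 does not support that. With a preoperative, a three-month and yearly measurements, its mixed-model sentence fits these endpoints, and such a model can take the preoperative score. The Synopsis also puts the emphasis on multivariable methods. What remains is that the text does not say the score will be used.
- The lists in 4.2 are not a closed set. Section 4.3 promises demographic adjustment, yet age at diagnosis and sex are on neither list. Covariates for each model are often left to an analysis plan, which is not at hand. Still, the protocol does fix lists by expected influence, and the endpoint's own baseline is an odd omission from them.
- A reader might infer that follow-up comparisons are confounded. The documents do not show it. Section 2.8.1.1 ties strategy to tumour position, and hypothalamic involvement is a mandatory factor. Hydrocephalus, visual deficits, symptoms and cognition are potential factors and partial proxies. Section 8.6 reports a correlation of 0.7 between FMH and IQ. The ρ × δ figures therefore describe an otherwise unadjusted comparison and would shrink in the adjusted models.
- A reader might also infer a sure loss of precision. Step 4 shows that adjustment can lose precision when the baseline is incomplete, and section 6 only proposes its preoperative diagnostics.

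**Conclusion.** The omission stands. The endpoints' own preoperative scores are requested as a baseline and preoperative function is named as prognostic, but the scores are on neither list and have no stated role in comparing strategies. The consequence is possible residual confounding, not demonstrated confounding.

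For an otherwise unadjusted comparison the bias is 0.06 to 0.35 SD over the assumed ranges of ρ and δ, and smaller where listed factors carry the same information. A precision gain is conditional: at 41/70 coverage without imputation it appears only above ρ of about 0.64. None of these values of ρ, δ, effect size or group size is in the protocol, and the coverage rate is borrowed from the predecessor study.

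The analysis is mainly descriptive and all inference is exploratory, so no confirmatory claim is damaged. The change is still worth making, because an exploratory result biased in this way suggests the wrong hypothesis about strategy.

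**What to change.** - **Section 4.2 (and Synopsis):** for the FMH, PedQol and PedsQL endpoints, add the preoperative score of the same instrument as a factor.
- **Section 4.3:** state that strategies are compared on these endpoints by a linear mixed model with the preoperative score as first repeated measure and a strategy-by-time term. This keeps patients without a baseline and needs no imputation, so it agrees with 4.4.
- **Sensitivity analysis:** adjust for the preoperative score as a covariate, in patients who have one or with multiple imputation, which 4.4 allows at this level but not in the primary analyses. Report both results, since they differ when the groups start apart (step 5).
- **Section 4.3:** treat the t-test and Mann-Whitney comparisons of these endpoints as descriptive.

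The cost is a few lines of text and no new data collection. The downside is that preoperative QoL will be incomplete, so the result relies on a missing-at-random assumption for patients without a score. The number with a preoperative score should be reported by strategy.

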4.4. Treatment of missing values and outliers

For the primary analyses no imputation of missing values will be applied. Number of patients with missing data and missingness patterns will be presented descriptively. In additional sensitivity analyses multiple imputation approaches or models applicable to longitudinal data with missing values (e.g., linear mixed models) can be used. Results will be compared and discussed. In case of time-to-event enpoints missing data will be treated as right-censored.

4.5. Software

Statistical analyses will be performed using standard statistical software like SAS or SPSS.

5. Documentation

Of particular importance is the grading of preoperative hypothalamic involvement and postoperative assessment of hypothalamic lesions by pre and postoperative imaging (MRI + as needed native CT)!

Documentation is oriented towards standardization of data collection already initiated in KRANIO-PHARYNGEOM 2000 and HIT-ENDO. It consists of:

Registration forms for German Childhood Cancer Registry

These forms are available at the participating centers. There is one registration form for all malignant diseases as well as for all central nervous system (CNS) tumors (regardless of ranking), which should immediately be sent to the Institute for Medical Biometrics, Epidemiology and Medical Informatics (DKKR), Mainz. DKKR will then send the craniopharyngioma assessment forms to the centers.

Craniopharyngioma assessment forms

Craniopharyngioma assessment forms in KRANIOPHARYNGEOM Registry 2019 should be filled out and then sent to the study's administration. They should include: patient age, preoperative symptom(s), symptom(s) duration, patient's anthropometric data, patient's endocrine condition, primary tumor location and size, surgical strategy (intended complete/incomplete resection), and size of any postoperative residual tumor remnant.

Data assessment forms (see also Appendix section16)

- Data of Diagnosis (CRF 1)
- Neurosurgery Recording Form (CRF 2)
- Radiotherapy Recording Form 1.0 General Information (CRF 3)
- Radiotherapy Recording Form 1.1 Treatment Technique (CRF 3)
- Consignment bill sending radiological Images to the Radiological Reference Center Augsburg (CRF 4)
- Follow-up Recording Form (CRF 5)
- Status, Relapse and Death (CRF 6)
- Radiological Reference Evaluation Recording Form (CRF 7)
- Report of serious adverse events Recording Form (CRF 8)

Copies of **physician letters** regarding the usual patient care information should be sent to the study's administration.

Reference histology: Reference-assessed histological findings will be sent to the corresponding pathologist/neuropathologist, the recruiting hospital, and study coordinator.

Reference radiology: Original CT and MRI images of the initial postoperative examination should to be sent via telematik platform (MDPE-Server) to the neuroradiology reference center at University of Augsburg for study evaluation (Dr. [name], Neuroradiology Dept, Universitätsklinikum Augsburg). Imaging for monitoring of suspected progressions should also be sent to the reference center (Augsburg) for co-evaluation.

Reference assessment of imaging will be provided via telematic platform (MDPE).

Archiving study documentation is done by the study coordinator. Data collected in the contex of registration (DKKR) will be archived by the German Pediatric Cancer Registry.

Medical data relevant for the trial KRANIOPHARYNGEOM Registry 2019 will be documented by qualified staff at the participating sites. Data locally assessed will be documented soon after assessment into the eCRF. Entering data may be delegated to qualified members of the team. However, CRFs will be finally signed by an investigator.

The KRANIOPHARYNGEOM Registry 2019 coordinating office at Oldenburg is responsible for the data management of the registry. During data entry at the sites, automated plausibility checks are run. In addition, qualified staff at the KRANIOPHARYNGEOM Registry 2019 trial office will regularly check data

entries for plausibility and completeness. Discrepancies and implausabilities will be solved with the participating sites by queries.

6. Proposed preoperative diagnostics

All suggestions for pre and postoperative diagnostics, treatment and follow-up care are based on the official guidelines (AWMF-No: 025/026) on childhood-onset craniopharyngioma (for detailed information see Appendix section 21)

